5.1 Protocol requested treatment

5.1.1 Investigational treatment

The investigational drug in this study will be ranibizumab 0.5 mg.

Ranibizumab is formulated as a sterile solution aseptically filled in a sterile glass vial. Each

vial contains ranibizumab in an aqueous solution (pH 5.5) with histidine, trehalose, and polysorbate 20. The vial contains no preservative and is suitable for single use only.

Ranibizumab must be stored according to the label instructions and it must be kept in a secure locked facility. The vials must be kept away from direct sunshine and must be kept in a refrigerator between 2°C -8°C (36°F – 46°F) and must not be FREEZED.

No additional treatment beyond investigational treatment is requested for this trial.

5.2 Treatment arms

Patients will be assigned to one of the following “2” treatment arms randomly

A study-specific randomization scheme will be prepared by the CRO to follow up the randomization.

- Arm 1 - Labeled regime arm: Treatment will be given monthly and continued until maximum visual acuity is achieved (the patient’s visual acuity is stable for three consecutive monthly assessments performed while on ranibizumab treatment). Thereafter patients should be monitored monthly for visual acuity.

Treatment is resumed when monitoring indicates loss of visual acuity due to DME. Monthly injections should then be administered until stable visual acuity is reached again for three consecutive monthly assessments (implying a minimum of two injections). The interval between two doses should not be shorter than 1 month.

- Arm 2 - Wait and Extend regime arm: Lucentis (ranibizumab) 0.5 mg will be injected subsequently at baseline, month 1 and 2. After the three initial loading doses, patients will be called for control 1 month later. If the visual acuity has reached a stable level and there is no sign of edema on OCT, patients will not receive intravitreal injection and will be called to come back 6 weeks later. The interval is increased by 2 weeks until a maximum of 8 weeks as long as the patient presents as stable regarding visual acuity, central retinal thickness and clinical findings. If there is a negative change, the interval is shortened back to 4 weeks.

5.3 Treatment assignment, randomization

At Visit “2” an eligible patient will be given the lowest available randomization number. This number assigns the patient to one of the treatment arms. The investigator will enter the randomization arm on the CRF. Randomization will be performed in 1:1 ratio.

The randomization numbers will be generated using the following procedure to ensure that treatment assignment is unbiased and concealed from patients and investigator staff. A randomization list will be produced by or under the responsibility of the CRO via a special randomization scheme prepared study specific for this study.

5.4 Treatment blinding

The study is an open label study so there are no blinding procedures applicable.

5.5 Treating the patient

5.5.1 Patient numbering

Each patient is uniquely identified by a Subject Number which is composed by the site number assigned by Novartis and a sequential number assigned by the investigator. Once assigned to a patient, the Subject Number will not be reused.

Upon signing the informed consent form, the patient is assigned the next sequential number as given by the investigator using the next blank CRF book. If an enrolled patient fails to be randomized or treated for any reason, the reason will be entered on the related page of the CRF.

5.5.2 Dispensing the investigational treatment

Each study site will be supplied by Novartis with investigational treatment in packaging of identical appearance.

The investigational treatment packaging has a 2-part label. A unique medication number is printed on each part of this label which corresponds to the treatment arms, according to the confidential randomization list. Immediately before dispensing investigational treatment to the patient, investigator staff will detach the outer part of the label from the packaging and affix it to the source document (Drug Label Form) for that patient's unique patient number.

5.5.3 Handling of study treatment

5.5.3.1 Handling of investigational treatment

Investigational treatment must be received by a designated person at the study site, handled and stored safely and properly, and kept in a secured location to which only the investigator and designees have access. Upon receipt, all investigational treatment should be stored according to the instructions specified on the labels. Clinical supplies are to be dispensed only in accordance with the protocol.

Medication labels will be in the local language and comply with the legal requirements of each country. They will include storage conditions for the investigational treatment but no information about the patient except for the randomization number.

The investigator must maintain an accurate record of the shipment and dispensing of investigational treatment in a drug accountability log. Monitoring of drug accountability will be performed by the field monitor during site visits and at the completion of the trial. Patients will be asked to return all unused investigational treatment and packaging at the end of the study or at the time of discontinuation of investigational treatment.

At the conclusion of the study, and as appropriate during the course of the study, the investigator will return all unused investigational treatment, packaging, drug labels, and a copy of the completed drug accountability log to the Novartis monitor or to the Novartis address provided in the investigator folder at each site.

5.5.4 Instructions for prescribing and taking study treatment

All dosages prescribed and dispensed to the patient should be tracked in the related section of the CRF in each visit.

The investigator should promote compliance and the importance of the attendance to the study visits by instructing the patient to attend the study visits since the injections will be followed up during the study visits and by stating that compliance is necessary for the patient's safety and the validity of the study.

5.5.5 Permitted dose adjustments and interruptions of study treatment

Dose interruptions are permitted to achieve patient compliance and study completion. There are some guidelines that shows the below interruptions are suitable or not.

The guidelines showing the interruptions are suitable or not

Event	Dose interruption criteria
Intraocular Inflammation	Discontinue the medication if intraocular inflammation is $\geq 2+$. Study treatment will be allowed when intraocular inflammation returns to baseline or a better level.
Loss of Visual Acuity	Discontinue the medication if BCVA is decreased ≥ 30 letters compared to the baseline values as a result of the study treatment. Study treatment will be allowed when the change in BCVA returns back to ≤ 10 letters below the final BCVA assessment at the final injection before interruption of the medication.
Intraocular Pressure (IOP)	Discontinue the medication if IOP ≥ 30 mmHg in the study eye. Study treatment will be allowed when the IOP assessed by the investigator returns back to <30 mmHg level with treatment or spontaneously.
Vitreous Hemorrhage	Discontinue the medication if there is $\geq 2+$ vitreous hemorrhage and ≥ 30 letters decrease in BCVA compared to Baseline.
Rhegmatogenous Retinal Tears or Detachment	Discontinue the medication if there is retinal tear or detachment. The patient with grade 3 or 4 macular holes will not continue to the study treatment.
Intraretinal Hemorrhage	Discontinue the medication if there is intraretinal hemorrhage affecting the fovea and the size of the hemorrhage is equal to the 50% or more than the total lesion or ≥ 1 disc area.
Local or Systemic Infection	Discontinue the medication if one of the below occurs: If either of the two eyes has infectious conjunctivitis, keratitis, scleritis or if the patient receives active treatment for a systemic infection.
Intraocular Surgery	Discontinue the medication if there is an intraocular surgical intervention during the last 30 days.
Grade 2 Target Adverse Events	Discontinue the medication until the event returns back to Grade 1 or a better level.

These changes must be recorded on the Dosage Administration Record CRF.

5.5.6 Rescue medication

After 3 monthly injections of the investigational drug laser photocoagulation can be administered if VA worsens >10 letters and/or CRT increases >100 microns.

5.5.7 Concomitant treatment

Moxifloxacin (Vigamox®) drop will be administered to the injection eye after injection. The investigator should instruct the patient to notify the study site about any new medications he/she takes after the patient was enrolled into the study. All medications, procedures and significant non-drug therapies (including physical therapy and blood transfusions) administered after the patient was enrolled into the study must be recorded.

5.5.8 Prohibited Treatment

Any concomitant medications including prescription drugs or over-the-counter preparations used by a patient during the study and until the conclusion of the study participation (except for routine medications given for ocular procedures required by the protocol, i.e. fluorescein, dilating drops, topical antibiotic, topical anesthetic) must be recorded on the Concomitant medications/Significant non-drug therapies CRF including start and stop dates and reason for use.

Laser photocoagulation for DME is permitted only as rescue treatment according to predefined criteria and needs to be

recorded on the Concomitant medications/Significant non-drug therapies CRF

Use of the following treatments is NOT allowed after the start of the study:

- Chronic concomitant therapy with topical ocular corticosteroids
- Other intravitreal medication in the study eye
- Systemic medications known to be toxic to the lens, retina or optic nerve, including Deferoxamine, Chloroquine/ hydroxychloroquine (Plaquenil), Tamoxifen, Phenothiazines and Ethambutol
- Treatment with glitazones during the study.
- Any other investigational drug

The below treatments will be prohibited 30 days before randomisation: verteporfin (Visudyne®), external beam radiation treatment, , submacular surgery or other surgical interventions for DME.

The below treatments will be prohibited 90 days before randomisation: focal laser photocoagulation treatment.

The below treatments will be prohibited 120 days before randomisation: macular laser photocoagulation treatment.

During the study, below treatment will be permitted: Retrobulber anesthesia to prevent eye movements, metochloropamide or other treatments for preventing the nausea due to fluorescein injection and other routine treatments for glaucoma. The patient will also be provided an additional topical antimicrobial medication to use 3 days after the injection which will be used 4 times a day.

If the investigator decided that the other eye (other than the study eye) has a DME lesion or has a new DME lesion occurred during the study which needs treatment, appropriate routine ranibizumab treatment will be applied by the investigator; however any data will not be collected for the other eye. The ranibizumab treatment applied to the other eye will be given by NOVARTIS.

If a patient needs cataract surgery, the surgery must not be performed at least 28 days after last study treatment. After that, the next injection of the study medication should at least be performed 28 days after the cataract surgery. The patients should give every effort to comply to their normal examinations even in the surgery period that they did not receive the medication. The study medication must not be started if post-operative complications such as uveitis, cyclitis are seen after the cataract surgery.

The investigator should instruct the patient to notify the study site about any new medications he/she takes after the start of the study drug. All medications (other than study drug and routine medications given for ocular procedures required by the protocol) and significant nondrug therapies (including physical therapy and blood transfusions) administered after enrollment into this study must be recorded on the Concomitant medications/Significant nondrug therapies page of the CRF.

5.5.9 Discontinuation of study treatment and premature patient withdrawal

Ranibizumab treatment must be discontinued if the investigator determines that continuing it would result in a significant safety risk for that patient. The following circumstances **require** study drug discontinuation:

- Withdrawal of informed consent
- 3 missed doses of the study medication
- Pregnancy
- Occurrence of the below adverse events: Any grade 3 target adverse event, Grade 3 retinal tear or detachment, Grade 3 vitreous hemorrhage that is not cured (decrease as 1+ or below level) until the next planned injection date
- Any other protocol deviation that results in a significant risk to the patient's safety.
- Use of prohibited medication

In addition to these requirements for study drug discontinuation, the investigator should discontinue study drug for a given patient if, on balance, he/she thinks that continuation would be detrimental to the patient's well-being.

Patients who discontinue study drug should NOT be considered withdrawn from the study. The investigator should encourage the patient to continue the scheduled assessments of the final visit.

Patients may voluntarily withdraw from the study for any reason at any time. They may be considered withdrawn if they state an intention to withdraw, or fail to return for visits, or become lost to follow up for any other reason.

If premature withdrawal occurs for any reason, the investigator must determine the primary reason for a patient's premature withdrawal from the study and record this information on the Study Completion CRF.

For patients who are lost to follow-up (i.e. those patients whose status is unclear because they fail to appear for study visits without stating an intention to withdraw), the investigator should

show "due diligence" by documenting in the source documents steps taken to contact the patient, e.g. dates of telephone calls, registered letters, etc.

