Study/investigational treatment discontinuation	Point/time when patient permanently stops taking study/investigational treatment for any reason; may or may not also be the point/time of premature patient withdrawal
Variable	Information used in the data analysis; derived directly or indirectly from data collected using specified assessments at specified time points

Protocol synopsis

Protocol number	CRFB002DTR01
Title	A randomized, open-label non-inferiority study to compare safety and efficacy of labeled versus wait and extend regimen of Lucentis (ranibizumab) in Turkish patients with visual impairment due to diabetic macular edema.
Brief title	Study of efficacy and safety of Ranibizumab in Turkish patients with visual impairment due to diabetic macular edema.
Sponsor and Clinical Phase	Novartis / Phase III
Investigation type	Drug Research
Study type	Interventional Study
Purpose and rationale	
The purpose of this study is to demonstrate the non-inferiority of “wait and extend” regimen of ranibizumab to labeled posology in Turkish patients with visual impairment due to diabetic macular edema with respect to the mean change in BCVA at 12th month from baseline..
 
Data from RESOLVE and RESTORE trials supporting monthly assessments and PRN Lucentis injections assumed to be considered as “gold standard” for future treatment of patients with visual impairment due to diabetes macula edema as it is for wet AMD. However, there is a need to explore a more clinical feasible treatment regime to provide satisfactory treatment effect with a lower number of visits and injections. A “wait and extend” regimen has been demonstrated efficient for treatment of wAMD in SALUTE study as mentioned above and found to be safe and tolerable. The rationale of this pilot study is to show that similar approach is applicable in treatment of DME.

Primary Objective(s) and Key Secondary Objective	The primary objective of this study is to demonstrate the non-inferiority of “wait and extend” regimen of ranibizumab to labeled posology in Turkish patients with visual impairment due to diabetic macular edema with respect to the mean change in BCVA at 12 th month from baseline..

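### Protocol sections 5.5.5 and 5.5.9 use unaligned criteria for holding and stopping ranibizumab, and the acuity row of 5.5.5 can meet its stop and restart conditions at the same visit

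*Protocol*

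**What the plan says.** Protocol section 5.5.5 introduces its table as guidance on pauses: "Dose interruptions are permitted to achieve patient compliance and study completion". Its vitreous haemorrhage row has two conditions, both needed: at least 2+ "vitreous hemorrhage and" at least 30 "letters decrease in BCVA compared to Baseline". The row gives no condition for resuming.

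The loss-of-acuity row stops treatment when BCVA has fallen 30 or more letters from baseline because of study treatment. It allows treatment again once BCVA is no more than 10 "letters below the final BCVA assessment at the final injection before interruption of the medication".

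Section 5.5.9 is a mandatory list. One item is "Grade 3 vitreous hemorrhage that is not cured (decrease as 1+ or below level) until the next planned injection date". It carries no acuity condition.

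The glossary defines study treatment discontinuation as "Point/time when patient permanently stops taking study/investigational treatment for any reason". Every row of the 5.5.5 table nevertheless uses the verb *discontinue*. The SAP restates neither set of rules.

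**The concern.** The two sections deal with the same clinical events but were not written to fit together. One would expect any eye that must be stopped permanently to qualify also for a temporary hold. For vitreous haemorrhage this fails, because the hold has an acuity condition and the permanent stop has none. Within the acuity row, one would expect the restart condition to require some recovery from the state that triggered the stop. Because the two conditions use different reference values, it need not.

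What is at stake is mainly patient safety and uniform handling. Investigators apply these rules at the visit, in an open-label trial with approximately 12 centres. Whether an eye is injected, paused or permanently stopped should not depend on which of two pages the site consults.

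**Working it through.** No planned figure is involved, so there is nothing to reproduce. The check sets the rules side by side and then does simple arithmetic on the acuity row.

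**Vitreous haemorrhage.** Inputs: the 5.5.5 haemorrhage row (2+ or more, and a loss of 30 or more letters from baseline) and the 5.5.9 item (Grade 3, not down to 1+ or below by the next planned injection). Assumption: Grade 3 corresponds to 3+.

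| Grade at onset | At next planned injection | Letters lost from baseline | 5.5.5 haemorrhage row | 5.5.9 haemorrhage item |
|---|---|---|---|---|
| 3 | 2+ or 3+ | 10 or 29 | not met | permanent stop |
| 3 | 2+ or 3+ | 30 or 40 | hold | permanent stop |
| 3 | 1+ or less | any | not met | not met |
| 2 | 2+ | 10 or 29 | not met | not met |
| 2 | 2+ | 30 or 40 | hold | not met |

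The first line is the mismatch. In no line does one section order an injection that the other forbids. With 30 or more letters lost, the separate acuity row also applies if the loss is attributed to treatment.

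**Loss of acuity.** Let B be BCVA at baseline, V at the last injection and N now.

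- Stop condition: B − N ≥ 30, so N ≤ B − 30.
- Restart condition: V − N ≤ 10, so N ≥ V − 10.
- Both can hold at one visit when V − 10 ≤ B − 30, that is, when V ≤ B − 20.

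Example: B = 60, V = 38, N = 29, with the loss attributed to treatment.

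- At the last injection the loss was 60 − 38 = 22 letters. This is below 30, so the acuity row did not prevent that injection.
- Now 60 − 29 = 31, which is at least 30: the stop is met.
- Now 38 − 29 = 9, which is at most 10: the restart is met with no recovery.

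The example's baseline of 60 lies inside the eligible range of 39 to 78 letters (section 4.1).

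**Terminology and resumption.** The nine rows of 5.5.5 divide as follows.

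- Four say when treatment may resume: inflammation, acuity, intraocular pressure and Grade 2 target adverse events. They plainly describe pauses.
- Two describe a current state that lapses by itself: infection, and intraocular surgery in the last 30 days.
- Three give no resumption condition: vitreous haemorrhage, retinal tear or detachment, and intraretinal haemorrhage.

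For the last three the reader cannot tell a pause from a permanent stop. The tear row shows the effect. Read as permanent, it stops any tear or detachment, whereas 5.5.9 names only Grade 3. Read as a pause, it has no end.

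**The case against.** The strongest reply is that the sections do not conflict. Section 5.5.5 lists reasons to hold a dose and never says to inject when a row is unmet. Section 5.5.9 is mandatory, investigators are bound by the whole protocol, and 5.5.9 also has them stop whenever continuing would be a significant safety risk or detrimental. This stands as far as it goes. A reader might infer that the two sections give opposite instructions for the same eye; they do not, because silence is not an order to inject and both can be obeyed together. What remains is that no precedence or cross-reference is stated, and a site checking only the haemorrhage row would find no reason to withhold a dose that is due. The row is also looser than 5.5.9 on grade and timing; it is stricter only on acuity.

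On the acuity row, the restart wording speaks of returning to a level, which suggests a later visit after recovery. The overlap also needs an eye already 20 or more letters below baseline that is still being injected, with the loss attributed to treatment. Both remarks are fair and make the case uncommon. They do not remove the fault: in such an eye the restart condition demands no recovery at all.

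Four other stronger readings are not supported.

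- *Target adverse events.* Section 5.5.5 says of Grade 2 events "Discontinue the medication until the event returns back to Grade 1 or a better level", and 5.5.9 stops for "Any grade 3 target adverse event". If haemorrhage or inflammation were target events, further clashes would follow. The available text does not define the term, and a definition may lie in pages that are not public. Section 5.5.9 also lists Grade 3 haemorrhage separately, which would be redundant if it were a target event.
- *Falls from a peak.* An eye going from 50 at baseline to 75 and then 25 loses 50 letters yet is only 25 below baseline. That questions the choice of reference for a clinical threshold; it is not a contradiction.
- *Sole safeguard.* These are not the only rules for withholding: section 5.5.8 restricts injections around cataract surgery, and 5.5.9 has its discretion clause.
- *Missing resumption rules.* Counting the infection row as lacking a restart is debatable, since it describes a current state.

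**Conclusion.** The point holds as a misalignment to be reconciled. It has three parts:

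1. A Grade 3 vitreous haemorrhage not down to 1+ by the next planned injection, with fewer than 30 letters lost, meets the permanent-stop item of 5.5.9 but not the hold row of 5.5.5.
2. The acuity stop and restart conditions can both be true at one visit whenever BCVA at the last injection was 20 or more letters below baseline.
3. The table uses a word that the glossary makes permanent for what its heading calls interruptions, and three rows leave resumption open.

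The first part assumes that the Grade and + scales correspond. Section 5.5.9 mixes them in one criterion, section 7.1 grades adverse events by CTCAE, and the available text does not link them. If they do not correspond, a site cannot tell which eyes fall under both rules, which is itself a reason to fix the scale.

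A reader might go on to infer that the non-inferiority result is at risk. The documents do not support this. They give no frequency for haemorrhage or severe acuity loss, the same rules apply in both arms, and under 5.5.9 a patient who stops the drug is not withdrawn from the study. The matter deserves correction because it concerns safety and costs little.

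**What to change.** Reconcile sections 5.5.5 and 5.5.9 into one set of conditions per event (withhold, resume, permanently stop), or state which section governs and cross-refer. In doing so:

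- make sure that any eye meeting a permanent-stop condition also meets the matching withhold condition;
- word the acuity stop and resume conditions so that both cannot hold at the same visit;
- state for the vitreous haemorrhage, retinal tear or detachment, and intraretinal haemorrhage rows whether treatment may resume and, if so, when;
- use one named grading scale;
- use *interrupt* for pauses and keep *discontinue* for the glossary meaning.

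The sponsor's clinicians choose all thresholds; nothing here implies which existing rule is right. The cost is one protocol amendment to a table and a list, with a letter to sites. It adds no patients or procedures.
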